2. The physical exam should measure the spleen and liver, noting the maximal distance below the respective costal margins and should record the bi-dimensional diameter of the largest palpable node in each area of involvement including the following sites: left neck (sub-mandibular, cervical, supra-clavicular), right neck (sub-mandibular, cervical, supra-clavicular), left axillary, right axillary, left groin (inguinal, femoral) and right groin (inguinal, femoral).
3. Clinical response assessment: will be done per IWCLL criteria starting with evaluation of disease state at baseline and for progression of disease only every 3 cycles (for 36 cycles) during study treatment and every cycle (every 3 months) during follow-up without therapy.
4. CT scans should be done as clinically indicated for the management of the patient and in accordance with the IWCLL guidelines. CT scans may be done with patient's primary physician (if outside Mayo Clinic), results of these will be entered in the source document.
5. EKG or ECHO only if clinically indicated.
6. Hematology (CBC) / Serum Chemistry: During cycle 1 and 2, day 8 and 15 labs will be done at the treating physician discretion based on patient's clinical needs and/or can be done based on risk for TLS or for conduct of correlative studies. Monitoring for TLS is considered standard of care. In subsequent cycles CBC/chemistry will be done prior to beginning of each cycle as standard of care and additional testing will only be done as clinically indicated to be determined by treating physician. Laboratory workup may be done with patient's primary physician (if outside Mayo Clinic), results of these will be entered in the source document.
7. Quantitative immunoglobulin will be done at baseline and thereafter can be done every 4 cycles at the discretion of the treating physician and as per standard clinical practice.

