9.4 Treatment related lymphocytosis

Lymphocytosis has been reported with ibrutinib, however since this is a patient population who are already expected to be in remission post induction therapy it is not known if this lymphocytosis will still happen upon treatment with ibrutinib. Patients who develop this reaction will be monitored as per standard clinical protocol without specific intervention unless other specific symptoms / signs of disease progression is noted (such as increase in lymph node size that is progressive and persist beyond 3 months of

maintenance therapy, worsening of cytopenia from the time of initiation of maintenance therapy that is consistent with the IWCLL guidelines requiring therapeutic intervention, development of B symptoms persisting for more than 2 months while on therapy or other factors such as organomegaly demonstrating disease progression).

9.5

Medications to be used with caution

CYP3A-Inhibitors/Inducers: Ibrutinib is metabolized primarily by CYP3A. Avoid co-administration with strong CYP3A4 or moderate CYP3A inhibitors and consider alternative agents with less CYP3A inhibition.

If a strong CYP3A inhibitor (eg, ketoconazole, indinavir, nelfinavir, ritonavir, saquinavir, clarithromycin, telithromycin, itraconazole, nefazadone, or cobicistat) must be used, reduce ibrutinib dose to 140 mg or withhold treatment for the duration of inhibitor use. Subjects should be monitored for signs of ibrutinib toxicity.

If a moderate CYP3A inhibitor (eg, voriconazole, erythromycin, amprenavir, aprepitant, atazanavir, ciprofloxacin, crizotinib, darunavir/ritonavir, diltiazem, fluconazole, fosamprenavir, imatinib, verapamil, amiodarone, or dronedarone) must be used, reduce ibrutinib to 140 mg (for 840 mg/day dose, reduce to 280 mg) for the duration of the inhibitor use. Avoid grapefruit and Seville oranges during ibrutinib/placebo treatment, as these contain moderate inhibitors of CYP3A (see Section 5.3.1.2).

No dose adjustment is required in combination with mild inhibitors.

Avoid concomitant use of strong CYP3A inducers (eg, carbamazepine, rifampin, phenytoin, and St. John's Wort). Consider alternative agents with less CYP3A induction.

A comprehensive list of inhibitors, inducers, and substrates may be found at <http://medicine.iupui.edu/clinpharm/ddis/main-table/>. This website is continually revised and should be checked frequently for updates.

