11.2 Evaluation for Progression of Disease

11.21 **PROGRESSION (PD):** Patients will continue to receive protocol therapy unless they have evidence of disease progression according to the IWCLL criteria⁶ as evidenced by:

11.211 $\geq 50\%$ increase in the sum of the products of at least 2 lymph nodes on 2 consecutive determinations 2 weeks apart (at least one node must be ≥ 2

cm) that persist for > 3 months or the appearance of new palpable lymph nodes >1.5 cm not due to a tumor flare. Enlargements or the appearance of new nodes due to a tumor flare do NOT qualify as progression.

- 11.212 $\geq 50\%$ increase in the size of the liver and/or spleen as determined by measurement below the respective costal margin on 2 consecutive determinations 2 weeks apart and with a minimum of a ≥ 2 cm increase in size from baseline; or appearance of hepatomegaly or splenomegaly which was not previously present at baseline and not due to a tumor flare.
- 11.213 Transformation to a more aggressive histology (e.g. Richter's transformation).

Note: If a patient develops DLBCL at any time, it will be considered disease progression. If the patient develops any other hematologic malignancy while on study, it will not be considered progressive disease.

- 11.214 $\geq 50\%$ increase in the absolute number of circulating lymphocytes NOT due to infection, tumor flare or drug-associated lymphocytosis (taking as reference for progressive disease the smallest absolute lymphocyte count recorded since the treatment started). The absolute lymphocyte count must be at least $5000/\text{mm}^3$ to qualify as disease progression.
- 11.215 In the absence of progression as defined by 1, 2, 3, or 4 above, the presence of a ≥ 2 g/dl decrease in HGB, or $\geq 50\%$ decrease in platelet count or absolute neutrophil count will NOT exclude a patient from continuing the study. Work-up of such decreases to exclude auto-immune hemolytic anemia, pure red cell aplasia, or idiopathic thrombocytopenic purpura (ITP) should be considered.
- 11.216 For patients who achieve a CR or nodular PR, progression will be defined as recurrence of circulating leukemia cell clone and an ALC >5000 or recurrence of adenopathy >1.5 cm not due to a tumor flare.

11.22 **Not PD:** The patient was evaluated for progression only in this cycle and a formal response evaluation did not occur. The patient did not meet the criteria for progression per section 11.21.

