13.0 Treatment/Follow-up Decision at Evaluation of Patient

- 13.1 If the patient develops PD at any time during active treatment they will go to event monitoring. If the patient develops unacceptable adverse events, if the treating physician feels it is in the patient's best interest, or if the patient refuses all further study participation, study treatment will be discontinued, and the patient will go directly to event monitoring. Patients will then be followed in event monitoring per Section 18.0.
- 13.2 Patients not progressing on active treatment will continue treatment per protocol up to a maximum of 36 cycles. After the completion of 36 cycles, the patient will go to observation (maximum duration of observation 2 years). After completing observation, patients will enter event monitoring. NOTE: Patients who have residual disease at the end of 36 cycles will continue to event monitoring.
- 13.3 A patient is deemed ineligible if after registration, it is determined that at the time of registration, the patient did not satisfy each and every eligibility criteria for study entry. The patient may continue treatment off-protocol at the discretion of the physician as long as there are no safety concerns and as long as the patient was properly registered. The patient will go directly to the event-monitoring phase of the study (or off study, if applicable).
 - If the patient received treatment, all data up until the point of confirmation of ineligibility must be submitted. Event monitoring will be required per Section 18.0 of the protocol.
 - If the patient never received treatment, on-study material and the End of Active Treatment/Cancel Notification Form must be submitted. No further data submission is necessary.

Note: Due to the nature of the disease, if the patient is diagnosed with DLBCL within the first cycle of treatment, it will be assumed that the DLBCL was present at registration. The patient will be deemed ineligible per Sec 3.27.

- 13.4 A patient is deemed *cancel* if he/she is removed from the study for any reason before any study treatment is given. On-study material and the End of Active Treatment/Cancel Notification Form must be submitted. No further data submission is necessary.

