7. For patients whose only measurable disease at the time of enrollment is on CT scan, a CT scan demonstrating > 50% reduction of target nodes enlarged at baseline is required before classifying patients a PR.

C. **PROGRESSION (PD):** Patients will continue to receive protocol therapy unless they have evidence of disease progression according to the IWCLL criteria⁶ as evidenced by:

1. $\geq 50\%$ increase in the sum of the products of at least 2 lymph nodes on 2 consecutive determinations 2 weeks apart (at least one node must be ≥ 2 cm) that persist for > 3 months or the appearance of new palpable lymph nodes >1.5 cm not due to a tumor flare. Enlargements or the appearance of new nodes due to a tumor flare do NOT qualify as progression.
2. $\geq 50\%$ increase in the size of the liver and/or spleen as determined by measurement below the respective costal margin on 2 consecutive determinations 2 weeks apart and with a minimum of a ≥ 2 cm increase in size from baseline; or appearance of hepatomegaly or splenomegaly which was not previously present at baseline and not due to a tumor flare.
3. Transformation to a more aggressive histology (e.g. Richter's transformation).

Note: If a patient develops DLBCL at any time, it will be considered disease progression. If the patient develops any other hematologic malignancy while on study, it will not be considered progressive disease.

4. $\geq 50\%$ increase in the absolute number of circulating lymphocytes NOT due to infection, tumor flare or drug-associated lymphocytosis (taking as reference for progressive disease the smallest absolute lymphocyte count recorded since the treatment started). The absolute lymphocyte count must be at least $5000/\text{mm}^3$ to qualify as disease progression.
5. In the absence of progression as defined by 1, 2, 3, or 4 above, the presence of a ≥ 2 g/dl decrease in HGB, or $\geq 50\%$ decrease in platelet count or absolute neutrophil count will NOT exclude a patient from continuing the study. Work-up of such decreases to exclude auto-immune hemolytic anemia, pure red cell aplasia, or idiopathic thrombocytopenic purpura (ITP) should be considered.
6. For patients who achieve a CR or nodular PR, progression will be defined as recurrence of circulating leukemia cell clone and an ALC >5000 or recurrence of adenopathy >1.5 cm not due to a tumor flare.

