2. Complete response (CR) requires fulfillment of all physical exam and peripheral blood criteria for a duration of ≥2 months. A bone marrow aspirate and biopsy are required to document the response as a complete within two month of the formal response evaluation where clinical and laboratory evidence of complete response was first seen (see Section 11.21).

3. Patients who fulfill all criteria for a CR but who have a persistent anemia, thrombocytopenia, or neutropenia related to drug toxicity rather than residual CLL or have hypocellular marrow will be classified as CR with incomplete marrow recovery (CRI).
4. Nodular partial response (nPR) is essentially a patient who appeared to have a CR but nodules were present in the bone marrow. It requires fulfillment of all physical exam and lymphocyte criteria for CR; however, when the bone marrow is done to confirm CR, nodules of malignant lymphocytes are found. Patients must fulfill one or more of the blood count parameters (ANC, Platelets, Hemoglobin) but are not required to meet all 3 of these conditions. See Section 11.215 regarding the distinction between clonal and regenerative nodules.
5. Partial response (PR) requires fulfillment of at least two of the above-noted decrease in circulating lymphocytes, regression in adenopathy and regression in hepatosplenomegaly, and at least one other parameter listed above for a duration of ≥ 2 months. See Section 11.22.
6. Progression: Fulfilling the criteria as noted in section 11.23. Prior to the formal response evaluation, baseline on study measurements will be used to determine disease progression (e.g. not cycle by cycle comparisons). Once patients undergo formal response evaluation, the nadir value at either baseline or time of response will be used for evaluating future disease progression. In the absence of other indices of clinical progression, the presence of a ≥ 2 g/dL decrease in hemoglobin or a $\geq 50\%$ decrease in platelet count and/or absolute neutrophil count will not exclude a patient from continuing on the study. Although not mandatory, bone marrow aspirate and biopsy are strongly encouraged to better define the cause of the suppressed counts (e.g., treatment versus disease-related).

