7. Measurement of lymphadenopathy will be determined on physical exam by adding the sum of the products of the maximal perpendicular diameters of measured lesion(s). No simultaneous increase in the size of any lesions or the appearance of any new lesions may occur for 2 consecutive evaluations at least 1 month apart. Minor fluctuations are acceptable as long as they don't exceed 50% of previous measurement. However, if they do exceed 50% of the previous measurement, treatment should be held for 2 consecutive cycles to rule out the possibility of nodes that wax and wane. For purposes of determining CCR and nPR, all nodes on physical exam need to be ≤ 1.5 cm in maximal dimension or documented to be free of CLL by biopsy. NOTE: Information from CT scans regarding lymphadenopathy is not considered in the standard classification of response with the exception of the patients fitting criteria of section 11.218 and 11.227.
8. Measurement of hepatosplenomegaly will be determined by noting the maximal distance below the respective costal margins of palpable hepatosplenomegaly during rest (e.g., not during deep inspiration). NOTE: Information from CT scans regarding hepatosplenomegaly is not considered in the standard classification of response with the exception of the patients fitting criteria of section 11.218 and 11.227.

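### Appendix XII footnote 7 holds ibrutinib for two cycles after a nodal change of more than 50%, a hold that the progression and dosing sections do not call for

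*Combined protocol and SAP*

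**What the plan says.** Footnote 7 belongs to the Nodes row of the response table in Appendix XII E. It tolerates minor fluctuations up to 50% of the previous measurement. Beyond that, "if they do exceed 50% of the previous measurement, treatment should be held for 2 consecutive cycles to rule out the possibility" that the nodes merely wax and wane. The sentence before it concerns increases in lesion size, so growth is the natural reading. Section 7.1 sets the cycle at 28 days. Section 8.2 defines a hold as delayed dosing, with the delayed doses made up on restart.

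The texts that bear on the same patient are these:

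- Section 11.21, repeated in Appendix XII C: "Patients will continue to receive protocol therapy unless they have evidence of disease progression according to the IWCLL criteria".
- Section 13.2: "Patients not progressing on active treatment will continue treatment per protocol up to a maximum of 36 cycles".
- Section 11.0: suspected progression is worked up by examination, CT and blood counts, and confirmation at least 2 weeks apart is recommended. No hold is mentioned.
- Section 11.211 (same text in Appendix XII C, item 1): growth of existing nodes by 50% or more is progression only on "2 consecutive determinations 2 weeks apart (at least one node must be ≥ 2 cm) that persist for > 3 months".
- Appendix XII footnote 6: before formal response evaluation, "baseline on study measurements will be used to determine disease progression (e.g. not cycle by cycle comparisons"); afterwards the nadir is the reference.
- Section 8.2: an interruption for a reason other than toxicity must end within 90 days.
- Section 4.0 footnote 8(b): a hold of more than 21 days for any reason delays MRD testing so that 3 treatment cycles come before it.

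**The concern.** The footnote attaches a treatment action to a measurement rule, and the sections that govern treatment contain no such action. Sections 7 to 9 and 13 have no hold for node size, and no text says whether the appendix or the body takes precedence. Two sites could therefore manage the same patient differently.

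The trigger also does not match the event that it is meant to screen for. It uses the previous measurement, whereas progression uses baseline or nadir. It applies to nodes of any size, whereas Section 11.211 needs at least one node of 2 cm. And it removes the drug during the period in which persistence of growth is being judged. Continued growth could then reflect the interruption and not failure of ibrutinib, yet a finding of progression ends treatment under Section 13.1.

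**Working it through.** The plan gives no figure for this hold, so there is none to reproduce. The inputs are the 28-day cycle (7.1), the 2-cycle hold (footnote 7), the 3-month persistence rule (11.211), the MRD rule (4.0 footnote 8(b)) and the landmark definition (16.323 and 16.324).

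**Length of the hold.** 2 × 28 = 56 days. That is above the 21-day threshold that delays MRD testing and below the 90-day limit for non-toxicity interruptions. Taking 3 months as 91 days, and assuming that the hold starts when the growth is first seen, 56/91 = 62% of the persistence window is off drug.

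**Size of the trigger.** Nodes are compared by products of diameters. √1.5 = 1.225, so a 22.5% rise in each diameter reaches +50%. As an illustration, take two nodes palpated at 1.2 × 1.2 cm and later at 1.5 × 1.5 cm:

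- before: 2 × 1.2² = 2.88 cm²
- after: 2 × 1.5² = 4.50 cm²
- change: 4.50/2.88 − 1 = +56%, which exceeds the footnote 7 limit.

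No node reaches 2 cm, so Section 11.211 cannot call this growth progression. Section 11.216 does not either, because it needs adenopathy above 1.5 cm. Footnote 7 itself accepts these nodes for a clinical complete response: "all nodes on physical exam need to be ≤ 1.5 cm in maximal dimension or documented to be free of CLL by biopsy".

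**MRD tests around the 48-week landmark.** Without a hold, tests fall on days 84, 168, 252 and 336. On a calendar reading the window is 44 to 52 weeks, days 308 to 364. Let a 56-day hold start after cycle k (day 28k). Footnote 8(b) can be read in two ways:

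- Reading A, three cumulative treated cycles: every test due after day 28k moves by 56 days.
- Reading B, three cycles from restart: the next test is on day 28k + 56 + 84 = 28k + 140, then every 84 days.

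| Hold starts after cycle | Test in window, A | Test in window, B |
|---|---|---|
| 1, 4, 7 | day 308 | day 336 |
| 2, 5, 8 | day 308 | day 364 |
| 3, 6 | day 308 | day 308 |
| 9 | none (next 392) | none (next 392) |
| 10 | none (next 392) | none (next 420) |
| 11 | none (next 392) | none (next 448) |

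Day 392 is 392 − 364 = 28 days after the window closes. The patient stays in the landmark set, because only those who discontinue treatment before 48 weeks are excluded.

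**The same landmark read by cycles.** With doses made up, cycle 12 ends on day 336 + 56 = 392, and 4 weeks either side gives days 364 to 420. The tests on days 392 and 420 then fall inside. Only the cycle 11 case under reading B (day 448) falls outside. The landmark gap therefore depends mainly on taking 48 weeks as calendar time.

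**The case against.** The strongest objection is that continuing unless progression is shown cannot be meant literally. The protocol also holds drug for toxicity (8.2, 8.3), severe hepatic impairment (8.4), anticoagulation (9.5) and surgery (9.7), none of which requires progression. The phrase is better read as governing removal for progression, and Section 13.2 continues treatment as the protocol directs, which leaves room for holds. This stands: footnote 7 fits poorly with Section 11.21, but it does not flatly contradict it. The difference is that the other holds appear in the treatment sections with a safety reason. The nodal hold does not, and Section 11.0 already has a route for suspected progression that keeps the patient on drug.

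It is also fair to say that Appendix XII looks unreconciled with the body. It points to sections that the current body lacks, such as 11.23 and 11.218, and it asks for formal response every 2 cycles where Section 11.1 asks for progression only, every 3. The sentence may be a leftover. But the appendix speaks of continuing protocol therapy and of ibrutinib-associated lymphocytosis, and induction ended at least 56 days before registration (3.15). The only treatment left to hold is ibrutinib.

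The small-node example can be challenged, because the table lists nodes as absent for a clinical complete response, so 1.2 cm nodes may not count as measured lesions. Against that, Section 4.0 footnote 2 says that the examination "should record the bi-dimensional diameter of the largest palpable node in each area of involvement", with no lower size limit. The example shows what the wording permits, not how often it happens.

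Section 9.4 refers to "increase in lymph node size that is progressive and persist beyond 3 months" of maintenance therapy, but only for patients with treatment-related lymphocytosis, so it is not general support for the point.

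**Conclusion.** The point holds as an inconsistency of low severity. As written, footnote 7 interrupts ibrutinib for 56 days in a patient who need have neither toxicity nor progression, on a trigger that differs from the progression criteria in reference value and minimum node size. If it is followed, nodal persistence is judged largely off drug and MRD testing is delayed.

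A reader might infer more, and the documents do not support it:

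- That 56 days of drug are lost. Section 8.2 has held doses made up, and treatment is capped at 36 cycles, not by date.
- That the hold forces discontinuation. It is within the 90-day limit.
- That the landmark analyses are compromised. The gap arises for holds starting after cycles 9 to 11 on a calendar reading, concerns secondary endpoints only, and would follow any equally long hold through footnote 8(b).
- That the main result is at risk. The primary endpoint definition, the decision rule and the sample size do not change.

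The conclusion assumes that 'held' in the footnote carries the Section 8.2 meaning and that sites would act on the appendix. The documents give no rate of such nodal change, so no count of affected patients is claimed; it is probably small.

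**What to change.** Replace the hold sentence in footnote 7 with: 'If they do exceed 50% of the previous measurement, continue treatment and re-measure at least 2 weeks later; stop treatment for nodal growth only if PD per Section 11.21 is met.' Deleting the sentence alone would leave the 50% limit with no stated consequence. The replacement matches the confirmation interval in Sections 11.0 and 11.211 and leaves the other holds and stopping reasons as they are.

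The cost is one sentence at the next amendment. The re-measurement is the confirmation that Section 11.0 already recommends when progression is suspected, though a patient with small nodes may need an extra palpation between scheduled visits. No patients are added and the analysis does not change.
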